We aim to recruit 12 study participants and 5 control participants for this pilot study, which will be useful to 1) test the feasibility and acceptability of our methods and tools for later use on a larger scale, and 2) allow us to describe patterns in preliminary data to identify early associations that may guide the methodology of a larger study. A sample size of 12 study participants and 5 control participants is likely feasible, as the Orthopedic Clinic sees an average of 50 children for hip/spine surgery each year.

STUDY PROCEDURES

The study will include a total of six timed assessments (**Figure 1**). This includes three primary study assessments to collect functional survey and biomarker data: 1) at baseline (within three months of surgery), 2) 6 weeks post-operatively, and 3) 6 months post-operatively. Additionally, we will conduct three biomarker-specific collections during the time of surgery immediately prior to the initiation of the procedure, 12-24 hours post-operatively, and 1-2 weeks post-operatively, based on the physiology of the sequence of the innate and adaptive immune response systems. Most study assessments will be timed at standard of care visits at the BC Children's Hospital. Each primary study visit will take approximately 25-30 minutes. Total time of participation will be 1.5 – 2 hours. Measures will be taken congruently with standard clinical care data collection where possible to reduce participation burden. Some participants may be recruited exclusively for functional/quality of life data collection while the team awaits approvals for blood collection and storage, to allow for an increased sample size.

Baseline Data Collection

Study participants who have consented will undergo a total of 3 primary study visits and 6 biomarker collections (**Figure 1**). At Study assessment #1, demographic information for the child (including variables such as age, sex, race/ethnicity, primary diagnosis, GMFCS/CFCS/MACS score) and demographic information of the parent/caregiver (age, sex, relationship to child, employment status, household income, race/ethnicity, distance from home to primary medical facility) will be collected. Outcome measures (see below) will also be collected. Baseline data collection aims to capture the initial status of participants before any surgical intervention, providing a reference point for post-operative comparisons.

Outcome Measures

The follow study procedures correspond to our primary aims:

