- **Timepoint #1** (pre-operative appointment): during routine care through venipuncture by C&W Lab Technicians. An additional finger prick will be taken by technicians (non-routine).
- **Timepoint #2** (surgery): prior to incision through peripheral venous line by OR staff
- **Timepoint #3** (12-24 hours post-op): by bedside nurses in T6 or PICU
- **Timepoint #4** (1-2 weeks post-op)
 - Hip patients: non-routine collection by C&W Lab
 - Spine patients: by bedside nurses in T6
- **Timepoint #5** (6 weeks post-op): non-routine by C&W Lab
- **Timepoint #6** (6 months post-op): non-routine by C&W Lab

Participants may choose not to provide their blood samples and remain a participant for our functional questionnaire and quality of life-related data collection. Analysis of blood will be done in collaboration with the Core Facility for Neurology Biomarker Innovation/[name] Laboratory.

A 3 mL aliquot of the child's blood will be set aside for our study. This blood will be transferred to the appropriate collection tubes (heparin coated) to prevent clotting and will be transported to the BC Children's Hospital BioBank for storage.

A lancing device will be used for finger capillary sampling to collect 50uL of blood from the child. The blood sample will be immediately collected following puncture using capillary tubes and transferred into pre-labeled collection tubes (heparin coated to prevent clotting) and mixed to ensure the sample remains homogeneous. After collection, the sample will be stored at -80 C at the BC Children's Hospital BioBank.

Blood collection of control participants

Control participants will only have their blood drawn at three timpoints. Relative to study participants, blood samples will be collected from controls at:

- **Timepoint #2** (surgery): prior to incision through peripheral venous line by OR staff
- **Timepoint #3** (12-24 hours post-op): through routine venipuncture in T6
- **Timepoint #6** (6 months post-op): non routine bloodwork by C&W lab

At the conclusion of data collection, all blood samples will be transported to the UBC [name] Laboratory (coordinated by the BC Children's Hospital BioBank).

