In collaboration with facilities and technologies of the UBC [name] Lab, biospecimens will be analyzed on the Alamar Biosciences ARGO HT platform, a fully automated immunoassay platform designed for Nucleic acid Linked Immuno-Sandwich Assay (NULISA) technology. The NULISA technology is a ligation-based assay which suppresses assay background using a dual capture and release mechanism with oligonucleotide-conjugated antibodies. It is designed to detect proteins across a high dynamic range with high sensitivity through next-generation sequencing of barcoded reporter DNA produced by the assay which also allows high multiplex capability. Analysis will include relative quantitation of a panel of 120 analytes designed to profile major hallmarks of central nervous system diseases (CNS) using the NULISAsq CNS Panel 120 assay. This assay is commercially available from Alamar Biosciences, and has been validated for sensitivity, precision, cross-lot, and cross-machine performance. Validation testing includes dynamic range, specificity, spike recovery, dilution linearity, sensitivity, intra-run, inter-plate, and inter-lot precision and accuracy. Each NULISA assay run contains 4 negative controls (NCs), 3 sample controls, 3 inter-plate controls (IPCs), and up to 86 samples. Each sample is spiked with the same concentration of an internal control (IC) used in the normalization procedure and as a method for assessing the uniformity of the assay run. IPC samples are pooled plasma controls used to normalize samples between experiments and to assess performance of the assay. NC wells are reactions where no sample input is provided and is used to assess limit of detection (LOD) for each target assay and to assess run quality. SC samples are pooled plasma controls from an independent source different from IPCs. SCs are used for calculating intra- and inter-plate coefficient of variation (CV). Specimens are assayed in singlicate in randomized order with no dilution required. Quality control measures, including but not limited to, CV of spiked IC signal across all samples, CV of the total assay signal across all IPCs, Median CV of all IPC targets, and percentage of targets that are detectable, defined as detectable if > 50% samples have signal > limit of detection, are recorded every run. Raw sequencing reads are processed to generate target- and sample-specific counts called NULISA Protein Quantification (NPQ) values. The raw sequencing reads are first normalized to the IC to control for well-to-well variation and then normalized to the median IC-normalized counts for the IPC samples for plate-to-plate variation.

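### A second assay run is possible at the planned sample count, and the protocol's layout rule does not keep a child's serial blood samples on one plate (minor)

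*Protocol*

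**What the plan says.** All of this is in the protocol.

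- **Participants** (Sample Size Justification): "We aim to recruit 12 study participants and 5 control participants for this pilot study".
- **Draws per SNI child** (Study Procedures, Baseline Data Collection): these children "will undergo a total of 3 primary study visits and 6 biomarker collections".
- **Draws per control** (Blood collection of control participants): "Control participants will only have their blood drawn at three timpoints", namely Timepoints #2, #3 and #6.
- **Finger prick** (Blood collection of study participants): listed for SNI children at Timepoint #1 only, "An additional finger prick will be taken by technicians (non-routine". It is stored at the BioBank. The protocol does not say whether it is assayed as a separate sample beside the venous one.
- **Run capacity** (Data Analysis, Blood collection): besides 4 negative controls and 3 sample controls, one run takes "3 inter-plate controls (IPCs), and up to 86 samples".
- **Layout** (same section): "Specimens are assayed in singlicate in randomized order with no dilution required".

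The assay section also provides for more than one plate. Sample controls are used to calculate the coefficient of variation within and between plates, and counts are normalised to the median of the inter-plate controls (IPCs). No total sample count and no number of runs is stated.

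**The concern.** The full planned count is just above the capacity of one run, and clearly above it if the finger pricks are assayed. If a second run is used, the layout decides where any remaining plate difference goes. The randomisation rule is worded for specimens, and nothing in it holds a child's series together or spreads SNI and control children over plates.

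Two biomarker questions would be affected. The first is the pre- to post-operative change within a child, which picks up a between-plate component when the child's samples lie on two plates. The second is the SNI versus control comparison at each timepoint, where five control samples could fall unevenly over plates. Each specimen is measured once, so there is no within-child replicate from which to separate that component. Samples are shipped together when data collection ends, so the whole layout can be planned in advance; it cannot be changed after the assay.

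**Working it through.** **1. Capacity.** The wells described for one run sum to 4 + 3 + 3 + 86 = 96, so 86 is consistent with the listed controls.

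**2. Planned samples.**

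- SNI venous: 12 × 6 = 72
- Control venous: 5 × 3 = 15
- Venous total: 72 + 15 = 87, one above 86
- With 12 finger pricks assayed separately: 87 + 12 = 99, thirteen above 86

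Either total would need two runs if every sample were obtained.

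**3. When a second run is needed.**

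- Venous only: one missing sample brings 87 to 86. One SNI child giving no blood leaves 87 − 6 = 81. So a second run is needed only at 100% collection.
- With finger pricks: 86/99 = 86.9%, so a second run is needed only above about 87% collection. Two SNI children giving no blood leave 99 − 2 × 7 = 85.
- At exactly 85% collection, the threshold that the protocol's outcome-completion criterion must exceed, the expected counts are 0.85 × 87 ≈ 74 and 0.85 × 99 ≈ 84. Both fit one run.

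As an illustration, suppose all 17 children give blood and samples are missing independently (an assumption):

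| Collection | P(all 87 obtained) | P(more than 86 of 99) |
|---|---|---|
| 85% | below 0.0001% | 26% |
| 90% | 0.01% | 81% |
| 95% | 1.2% | 99.9% |
| 99% | 42% | above 99.9% |

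**4. Chance that a child's series is split.** Assume that order is randomised across two plates holding n1 and n2 of N samples. For a child with m samples,

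P(split) = 1 − [C(n1, m) + C(n2, m)] / C(N, m).

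| N and fill | SNI child | Expected of 12 | Control (m = 3) |
|---|---|---|---|
| 87 as 86 + 1 (m = 6) | 6/87 = 6.9% | 0.83 | 3/87 = 3.4% |
| 87 as 44 + 43 (m = 6) | 97.4% | 11.7 | 75.9% |
| 99 as 86 + 13 (m = 7) | 63.9% | 7.7 | 34.6% |
| 99 as 50 + 49 (m = 7) | 98.8% | 11.9 | 75.8% |

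In the 86 + 1 case exactly one child is split: 12 × 6/87 + 5 × 3/87 = 0.83 + 0.17 = 1. For 44 + 43 and m = 6: 1 − (7,059,052 + 6,096,454)/504,981,379 = 0.974. The protocol does not say how plates would be filled.

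**5. Control samples at one timepoint.** With 87 samples as 44 + 43, the five control samples at a given timepoint fall 4–1 or 5–0 over the plates with probability 36%.

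**6. What a split could cost.** The residual plate error is not given, so only an illustration is possible. Assume that IPC wells carry the same random error variance σ² as sample wells, that errors are normal, and that there are no other plate effects. The median of three wells then has variance of about 0.45σ². A difference taken across two plates carries 2 × 0.45σ² = 0.90σ² from normalisation, on top of 2σ² of assay error: 0.90/2 = 45% more assay variance. This excludes biological variation, so the effect on the total variance of a change is smaller.

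**7. The constraint is feasible.** Put 6 SNI children on each plate and divide the controls 3 and 2.

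- Venous only: 6 × 6 + 3 × 3 = 45 and 6 × 6 + 2 × 3 = 42, total 87
- With finger pricks: 6 × 7 + 3 × 3 = 51 and 6 × 7 + 2 × 3 = 48, total 99

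All plates are under 86 and no child is split.

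**The case against.** The strongest reply is that the protocol contains no error here. It never says that one run is enough, so the figure of 86 contradicts nothing. A reader might infer that the plan randomises specimens without restriction over plates. The text does not say so: random order within a plate, with each child's samples kept together, fits it equally well. Plate maps also often sit in laboratory documents that are not shown. This stands, and it makes the point one of clarity and not of contradiction.

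A reader might also infer that a second run is inevitable, or that nearly every SNI child would be split. Neither follows. Blood is optional, and some participants may be recruited for function and quality of life only. Recruitment on the day of surgery comes after the pre-operative appointment at which the first sample is drawn. The count of 99 depends on finger pricks being assayed separately. The 97.4% depends on near-equal plates, which the protocol does not specify; filling the first run with 86 of 87 samples splits one child.

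Third, plate differences are not ignored. Sample controls estimate variation between plates, IPC normalisation reduces it, and inter-plate precision has been validated. It would be wrong to say that run-to-run error could not be detected; singlicate assay only means that it cannot be seen child by child. Random order also adds noise and not systematic bias, and the Data Analysis section describes the inflammatory results as patterns in a small sample. All of this stands and lowers the weight of the point. It does not remove it: the stated rule allows the poor layout as readily as the good one, and normalisation to three wells carries error of its own.

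**Conclusion.** The point holds in a limited, conditional form and is minor. The full plan gives 87 venous samples, or 99 with finger pricks assayed separately, against 86 per run. A second run is needed only at 100% venous collection, or above about 87% collection of the 99. If there are two runs and order is randomised across them, between one child and nearly all SNI children would have a split series, depending on how plates are filled.

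The consequence is added noise in the within-child change, and possibly uneven plates in the group comparison. Its size cannot be derived from the protocol; the 45% increase in assay variance is an illustration under stated assumptions. The primary feasibility and acceptability outcomes are not affected. With a single run the issue does not arise.

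**What to change.** Add to the assay section:

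1. whether the Timepoint #1 finger-prick samples are assayed as separate samples;
2. that, if more than one run is needed, all samples from one child go on the same plate, SNI and control children are balanced over plates as evenly as possible, and order is randomised within plate.

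The cost is a sentence or two and a plate map drawn up once the final sample count is known. The layout becomes more constrained, and any remaining plate effect moves from within children to between children. That is why group balance matters, and with five controls over two plates the best available division is 3 and 2. No run is added beyond what the sample count itself requires.

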“Major” orthopedic procedures are defined, for the purposes of this study, as operations that are equal to or greater than 90 minutes in “skin-to-skin” time (initial incision to skin closure). Orthopedic procedures (hip reconstruction and spine stabilization) are the most common major procedures that

children with SNI are exposed to, although they also experience many “minor” procedures, such as gastrostomy tube placement, tendon releases, and dental procedures. We are focusing on the longer procedures for this pilot study both because anecdotally, parents have not described the same degree of concern with shorter operations, and for methodological reasons, to improve the opportunity to identify this phenomenon.

Study participant eligibility criteria

Inclusion Criteria

- 1) Children with SNI, including the Gross Motor Function Classification System (GMFCS) levels II to V and Communication Function Classification System (CFCS) levels II to V, and;
- 2) undergoing major orthopaedic surgical management of musculoskeletal pathology (spine or hip; major defined as a greater than or equal to 90 minute procedure with skin-to-skin contact) at the BC Children's Hospital and;
- 3) between 5 and 18 years at the time of their surgical procedure

Exclusion Criteria

- 1) GMFCS level I and CFCS level I
- 2) Non-English-speaking Parents/Caregivers

Control group - justifications and eligibility criteria

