We aim to recruit 5 control participants specifically for our biomarker analysis (ie. we will only collect demographics and blood samples). The inclusion of this control group allows for a direct comparison of the pre-, peri-, and post-operative inflammatory responses between children with SNI vs neurotypical patients undergoing similar procedures. This is essential for discerning whether any observed altered biomarkers levels specific to children with SNI (ie. and not seen in neurotypical patients), or if they reflect a generalized postoperative inflammatory response. This comparison strengthens the interpretation of our biomarker findings by providing a baseline, which will reduce the risk of misattributing inflammation-related findings solely to the presence of SNI rather than the general surgical response. Additionally, the inclusion of controls improves the clinical relevance of our study, as it will help determine whether children with SNI exhibit exaggerated, prolonged, or distinct inflammatory responses compared to their neurotypical counterparts. These insights will be critical for guiding future research and potential interventions aimed at mitigating PoFD in children with SNI.

Inclusion Criteria

- 1) Neurotypically developing children (GMFCS I and CFCS I)
- 2) Undergoing major orthopaedic surgical management of musculoskeletal pathology (spine or hip; major defined as a greater than or equal to 90 minute procedure with skin-to-skin contact) at the BC Children's Hospital
- 3) Between 5 and 18 years of age at the time of their surgical procedure

Exclusion Criteria

- 1) Non-English-speaking parents/caregivers

Participant Screening and Recruitment

Participants for this study will be recruited in-person through the BC Children's Hospital Orthopaedic Clinics, including the Orthopedic Cerebral Palsy Clinic (CP Clinic) and the Spine Clinic. Study participants

will receive \$100 remuneration for their participation in the study, and control participants will receive \$50 remuneration for their participation.

Participant Screening

1) Screening through standard-of-care clinical visits

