
With respect to statistical analysis of our control group, our primary analysis will involve a group comparison at each timepoint to assess whether, and to what extent, any biomarkers are altered (increased or decreased) in children with SNI compared to our controls. Given the large biomarker panel (approximately 120 biomarkers), data visualization using volcano plots will be employed. Multiple comparison adjustments will be applied using the false discovery rate (FDR) correction method (Benjamini-Hochberg). Biomarker significance will be determined based on effect size thresholds, specifically log2(fold change), with a significance level set at 5% (Type I error). Additionally, associations between biomarkers and study variables (e.g., age, sex) will be explored using Wilcoxon rank-sum tests.

Outcomes

The following outcomes will be utilized to deem our study feasible and acceptable:

Feasibility:

1. Consent rate: An average consent rate of 2-3 children/month
2. Protocol delivery: The protocol can be implemented with >85% protocol delivery.
3. Outcome completion: >85% of outcomes will be complete and measured as scheduled.

Acceptability:

4. General positive report on participation based on semi-structured interview

Secondary outcomes; we will explore pre- and post-operative data to describe patterns in:

1. Function of the child, as scored on the CPCHILD;
2. Quality of life of caregiver, as described by supplemental question;
3. Inflammatory profile of child

DATA STORAGE

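### The two-group Wilcoxon rank-sum test is named for associations of biomarkers with age, which the protocol never divides into groups

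*Protocol*

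**What the plan says.** The last sentence on biomarker statistics (protocol, DATA ANALYSIS, Blood collection) reads: "associations between biomarkers and study variables (e.g., age, sex) will be explored using Wilcoxon rank-sum tests". Age is its first example. No other method is named there for a continuous covariate.

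Elsewhere age is never grouped:

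- Children with SNI are eligible if "between 5 and 18 years at the time of their surgical procedure" (Study participant eligibility criteria).
- Controls are eligible if "Between 5 and 18 years of age at the time of their surgical procedure" (Control group).
- Baseline Data Collection lists age as a demographic item without categories.
- The only strata defined under DATA ANALYSIS are the sub-categories of GMFCS 5, which do not involve age.

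The target is 12 children with SNI and 5 controls (Sample Size Justification). Blood samples may be fewer. STUDY PROCEDURES says "Some participants may be recruited exclusively for functional/quality of life data collection while the team awaits approvals for blood collection and storage", and the section on blood collection of study participants adds "Participants may choose not to provide their blood samples". For controls, "Control participants will only have their blood drawn at three timpoints", namely timepoints 2, 3 and 6.

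**The concern.** The rank-sum test asks whether a response tends to be larger in one of two independent groups. With sex as the grouping variable the question is well posed. With age in years there are no two groups, so the named test cannot be run as written. An analyst would have to invent a cut-point.

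That has two consequences. Children on the same side of the cut are treated as having the same age, so part of the age information is lost in a sample that is already very small. The result also depends on the cut, and a cut left open can be chosen after the data are seen.

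What is at stake is modest. One stated purpose of the pilot is to "describe patterns in preliminary data to identify early associations that may guide the methodology of a larger study". An age trend in a marker across childhood and adolescence is one such association, and the named method is poorly suited to showing it.

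**Working it through.** The protocol gives no power figure for this analysis, so there is nothing of its own to reproduce. The check has two parts.

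**1. Does the named test fit the variable?**

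| Variable | Form in the protocol | Two groups available? |
|---|---|---|
| Sex | demographic item, treated here as two-level | yes |
| Age | 5 to 18 years, no bands or cut-point | no |

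The test fits sex. It fits age only after a split that the protocol does not define.

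**2. What does a split cost?**

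Inputs from the protocol: ages 5 to 18; 12 children with SNI; 12 + 5 = 17 if controls are pooled; 5% level.

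Assumptions, not in the protocol: ages uniform over the range, linear effect with normal error, one marker, two-sided test, no multiplicity adjustment. The sizes n = 10 and n = 8 stand for lower blood uptake. The case n = 17 assumes no group effect.

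Model: x = (age − 11.5) / (13/√12) and marker = ρ·x + √(1 − ρ²)·e, with e standard normal. For ρ = 0.6, √(1 − 0.36) = 0.8, so marker = 0.6·x + 0.8·e.

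Tests compared: Spearman correlation on age in years, with its cutoff from the permutation distribution (for example |r| ≥ 0.738 at n = 8), against the exact rank-sum test after a median split. There were 40,000 simulated samples per cell.

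Power at ρ = 0.6:

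| n | Spearman | Rank-sum, median split | Loss (percentage points) |
|---|---|---|---|
| 12 (6 v 6) | 52% | 35% | 52 − 35 = 17 |
| 10 (5 v 5) | 42% | 24% | 42 − 24 = 18 |
| 8 (4 v 4) | 29% | 15% | 29 − 15 = 14 |
| 17 (8 v 9) | 72% | 55% | 72 − 55 = 17 |

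Range over the assumed correlation (Spearman v rank-sum):

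| n | ρ = 0.4 | ρ = 0.6 | ρ = 0.8 |
|---|---|---|---|
| 12 | 22% v 16% | 52% v 35% | 90% v 71% |
| 10 | 18% v 10% | 42% v 24% | 81% v 51% |
| 8 | 13% v 7% | 29% v 15% | 63% v 33% |

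Spearman has more power in every cell. The gap is small where both tests are weak and wider for strong trends.

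**Dependence on the cut.** A separate run (4,000 samples, n = 12) compared a median split with a fixed cut at age 12. Power was 24% v 27% at ρ = 0.5 and 51% v 56% at ρ = 0.7. Spearman (p-values from the standard software approximation) gave 36% and 74% in the same run. The choice of cut changes the answer, and neither cut recovers the loss.

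**The case against.** The strongest reply is that this is one exploratory sentence in a pilot, with age given only as an example. DATA ANALYSIS already says that the sample is too small to confirm correlations of functional decline with biomarkers. The aim of finding early associations is study-wide and does not single out age. A statistical analysis plan that is not shown might also define age groups or name a test for each variable.

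Most of this stands, and it sets the weight. It does not remove the mismatch. The protocol does not leave the method open: it names a two-group test and applies it to age. A cut-point added later would make the test runnable but would still discard information.

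Some stronger readings are tempting and are not supported.

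- *False discovery rate.* A reader might infer that, with about 120 markers, the coarse p-values of a rank-sum test in so small a sample make any age finding impossible after adjustment. The protocol places the Benjamini-Hochberg correction with the comparison of SNI and control children and does not say that it covers these explored associations. The coarseness comes from small groups, so it would apply equally to sex, where the test is appropriate. It also eases if controls are pooled.
- *Sample of 12 at most.* A reader might take 12 as the limit. The sentence stands in the paragraph on the control group and does not restrict the associations to children with SNI. Pooling at shared timepoints could reach 17, and the power loss remains there.
- *Invalid p-values.* A reader might infer excess false positives. With the cut fixed in advance, the simulated rejection rate under no association was 4.6% at n = 12. The cost is power, unless the cut is picked from the data.
- *The 5% label.* The words "with a significance level set at 5% (Type I error" might suggest a second error-rate fault. They belong to the group comparison, and the sentence before them names the false discovery rate, so an adjusted p-value below 0.05 is the natural reading.

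**Conclusion.** The point holds in limited form: the stated test does not fit age, or any other continuous study variable, as written. It does fit sex. This conclusion comes from reading the text and needs no assumption.

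The size of the loss does rest on assumptions. With a true correlation of 0.6, a linear effect, uniform ages, one marker and an unadjusted two-sided 5% level, a median split costs about 14 to 18 percentage points of power for samples of 8 to 17. The correlation is assumed. Over 0.4 to 0.8, for samples of 8 to 12, the loss runs from about 6 to about 30 points.

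The weight is low. The analysis is exploratory, and no feasibility or acceptability outcome, nor the main comparison of SNI with control children, depends on it. It is worth correcting because the correction is so cheap.

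**What to change.** Replace the sentence with one that matches method to variable type. For age and any other continuous study variable, use Spearman rank correlation or regression. Do this within the SNI group, or with adjustment for group if controls are pooled at timepoints 2, 3 and 6, the only ones at which controls give blood. Keep the rank-sum test for sex and other two-level variables.

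The cost is one sentence of analysis text and no new data. The downside is small: Spearman correlation detects only monotone trends, and it gives no group medians to display. Power at these sample sizes stays limited for moderate correlations whichever method is used, so estimates should still be read as descriptive. If a split of age is wanted for another reason, its cut-point should be stated and justified before the biomarker data are seen.
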